12.7. Analysis of Urine Albumin/Creatinine Ratio and Urine Protein/Creatinine Ratio

The analysis value for urine albumin/creatinine ratio and urine protein/creatinine ratio is defined as the average of all the values obtained for a timepoint. The planned number of urine albumin/creatinine ratios and urine protein/creatinine ratios is three at each scheduled timepoint. The baseline value of the urine albumin/creatinine ratio and urine protein/creatinine ratio is defined as the average of the analysis values at the two screening visits, i.e.,

$$\text{Baseline urine albumin/creatinine ratio} = (R_1 + R_2)/2,$$

R_1 and R_2 are the average values at screening visits 1 and 2, respectively. The baseline urine protein/creatinine ratio is defined in the same fashion.

Change from baseline and change in natural log transformed analysis value of urine albumin/creatinine ratio and urine protein/creatinine ratio at each scheduled visit will be summarized descriptively for each disease group, cohort and treatment. Nine-five percent CIs for the mean change in both the original value and the log transformed value at each scheduled visit will be provided using t-distribution. For Cohort 2 and Cohort 3, the mean difference between OMS721 and vehicle and its 95% CI will also be provided for each visit using t-distribution.

12.8. Analysis of eGFR

eGFR will be calculated using the 4 equations in Table 3. Change in eGFR from baseline at each scheduled visit will be summarized descriptively for each disease group, cohort and treatment. Nine-five percent CIs for the mean change from baseline will also be provided using t-distribution. For Cohort 2 and Cohort 3, the mean difference between OMS721 and vehicle and its 95% CI will also be provided for each visit using t-distribution.

Table 3: eGFR Equations

Formula	SCr or SCyst Range ¹	Equation (mL/min/1.73 m ²)
MDRD		$175 \times \text{SCr (mg/dL)}^{-1.154} \times \text{age}^{-0.203} \times [0.742 \text{ if female}] \times (1.212 \text{ if African American})$
CKD-EPI-SCr		$141 \times \min(\text{Scr}/\kappa, 1)^{\alpha} \times \max(\text{Scr}/\kappa, 1)^{-1.209} \times 0.993^{\text{age}} \times 1.018 [\text{if female}] \times 1.159 [\text{if black}]$ where κ is 0.7 for females and 0.9 for males, α is -0.329 for females and -0.411 for males, min indicates the minimum of Scr/ κ or 1, and max indicates the maximum of Scr/ κ or 1
Female	SCr ≤ 0.7 mg/dL	$144 \times (\text{Scr}/0.7)^{-0.329} \times 0.993^{\text{age}} \times 1.159 [\text{if black}]$
	SCr > 0.7 mg/dL	$144 \times (\text{Scr}/0.7)^{-1.209} \times 0.993^{\text{age}} \times 1.159 [\text{if black}]$
Male	SCr ≤ 0.9 mg/dL	$141 \times (\text{Scr}/0.9)^{-0.411} \times 0.993^{\text{age}} \times 1.159 [\text{if black}]$
	SCr > 0.9 mg/dL	$141 \times (\text{Scr}/0.9)^{-1.209} \times 0.993^{\text{age}} \times 1.159 [\text{if black}]$
CKD-EPI-Cyst	SCyst ≤ 0.8 mg/L	$133 \times (\text{Scyst}/0.8)^{-0.499} \times 0.996^{\text{age}} [x0.932 \text{ if female}] \times 1.159 [\text{if black}]$
	SCyst > 0.8 mg/L	$133 \times (\text{Scys}/0.8)^{-1.328} \times 0.996^{\text{age}} [x0.932 \text{ if female}] \times 1.159 [\text{if black}]$
CKD-EPI SCr–Cyst		
Female	SCr ≤ 0.7 mg/dL and SCyst ≤ 0.8 mg/dL	$130 \times (\text{Scr}/0.7)^{-0.248} \times (\text{Scyst}/0.8)^{-0.375} \times 0.995^{\text{age}} [\times 1.08 \text{ if black}]$
	SCr ≤ 0.7 mg/dL and SCyst > 0.8 mg/dL	$130 \times (\text{Scr}/0.7)^{-0.248} \times (\text{Scyst}/0.8)^{-0.711} \times 0.995^{\text{age}} [\times 1.08 \text{ if black}]$
	SCr > 0.7 mg/dL and SCyst ≤ 0.8 mg/dL	$130 \times (\text{Scr}/0.7)^{-0.601} \times (\text{Scyst}/0.8)^{-0.375} \times 0.995^{\text{age}} [\times 1.08 \text{ if black}]$
	SCr > 0.7 mg/dL and SCyst > 0.8 mg/dL	$130 \times (\text{Scr}/0.7)^{-0.601} \times (\text{Scyst}/0.8)^{-0.711} \times 0.995^{\text{age}} [\times 1.08 \text{ if black}]$
Male	SCr ≤ 0.9 mg/dL and SCyst ≤ 0.8 mg/dL	$135 \times (\text{Scr}/0.9)^{-0.207} \times (\text{Scyst}/0.8)^{-0.375} \times 0.995^{\text{age}} [\times 1.08 \text{ if black}]$
	SCr ≤ 0.9 mg/dL and SCyst > 0.8 mg/dL	$135 \times (\text{Scr}/0.9)^{-0.207} \times (\text{Scyst}/0.8)^{-0.711} \times 0.995^{\text{age}} [\times 1.08 \text{ if black}]$
	SCr > 0.9 mg/dL and SCyst ≤ 0.8 mg/dL	$135 \times (\text{Scr}/0.9)^{-0.601} \times (\text{Scyst}/0.8)^{-0.375} \times 0.995^{\text{age}} [\times 1.08 \text{ if black}]$
	SCr > 0.9 mg/dL and SCyst > 0.8 mg/dL	$135 \times (\text{Scr}/0.9)^{-0.601} \times (\text{Scyst}/0.8)^{-0.711} \times 0.995^{\text{age}} [\times 1.08 \text{ if black}]$
1 SCr is serum creatinine in mg/dL; Scyst is serum cystatin in mg/L.		

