6. STUDY ENDPOINTS

The primary endpoints are:

- Safety and tolerability of OMS721 as assessed by AEs, vital signs, clinical laboratory tests, and ECGs

The secondary endpoints are:

- 24-hour urine protein change from baseline to 12 weeks
- Urine albumin/creatinine ratio change from baseline to 12 weeks
- Corticosteroid dose needed to maintain stable renal function (Cohort 1)
- PK concentration and PK parameters of OMS721
- PD measure of inhibition of *ex vivo* lectin pathway activation

The exploratory endpoints are:

- Urine protein/creatinine ratio by disease
- Serum creatinine by disease
- eGFR by disease calculated by the MDRD equation, the CKD-EPI equation using serum creatinine, the CKD-EPI equation using cystatin C, and the CKD-EPI equation using creatinine – cystatin C
- Occurrence of ADA and Nab
- Urine inflammatory markers by disease
- Duration of therapeutic response, if observed, defined as the number of the longest consecutive weeks that 24-hour urine protein < 50% of the baseline for up to 104 weeks (Cohort 3 only)

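### SAP Table 3 prints the creatinine race factor 1.159 in both cystatin-C-only eGFR rows, apparently a transcription error that would inflate that eGFR and its absolute change by about 15 to 16% in Black subjects

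*SAP*

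**What the plan says.** SAP section 6 lists among the exploratory endpoints "eGFR by disease calculated by the MDRD equation, the CKD-EPI equation using serum creatinine, the CKD-EPI equation using cystatin C", followed by the combined creatinine-cystatin version. Section 12.8 gives the formulas in Table 3. The race terms there are:

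- Creatinine only (CKD-EPI-SCr), all rows: factor 1.159, for example "144 \times (\text{Scr}/0.7)^{-1.209} \times 0.993^{\text{age}} \times 1.159 [\text{if black".
- Cystatin C only (CKD-EPI-Cyst), both rows: "0.996^{\text{age}} [x0.932 \text{ if female}] \times 1.159 [\text{if black".
- Combined (CKD-EPI SCr-Cyst), all eight rows: "0.995^{\text{age}} [\times 1.08 \text{ if black".

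The analysis is on the untransformed scale: "Change in eGFR from baseline at each scheduled visit will be summarized descriptively for each disease group, cohort and treatment", with t-based 95% intervals. For Cohorts 2 and 3, "the mean difference between OMS721 and vehicle and its 95% CI will also be provided for each visit using t-distribution". Section 12.8 states no log transform, unlike sections 12.6 and 12.7. The SAP's reference list is empty and the protocol writes out only MDRD (Appendix 19.1), so in these two documents Table 3 is the only specification of the cystatin equation.

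**The concern.** Two different markers carry an identical three-decimal race coefficient, while the equation that uses both markers carries a much smaller one. If each marker needed a 16% upward adjustment, an equation built on both would be expected to need a similar adjustment, not 8%.

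A wrong multiplier does not cancel from an absolute change. Mean change from baseline would be overstated for each Black subject, and a group or arm mean would depend on its racial mix. The cystatin version could then appear to differ from the other three eGFR versions because of a coefficient rather than because of kidney function. Groups are small (about 16 subjects over four diseases in Cohort 1, 10 in Cohort 2, 18 in Cohort 3), so one subject carries noticeable weight.

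**Working it through.** There is no derived figure in the plan to reproduce. The check is whether Table 3 is consistent with itself, and then what the factor does to the analysed quantity.

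**Inputs (all from SAP Table 3).** Creatinine only: constant 141 (male) or 144 (female), exponent −1.209 above the cut-off, age 0.993, race 1.159. Cystatin only: constant 133, exponent −1.328 above the cut-off, age 0.996, female 0.932, race 1.159 ("133 \times (\text{Scys}/0.8)^{-1.328} \times 0.996^{\text{age"). Combined: constant 135 (male) or 130 (female), exponents −0.601 and −0.711 above the cut-offs, age 0.995, race 1.08 ("130 \times (\text{Scr}/0.7)^{-0.601} \times (\text{Scyst}/0.8)^{-0.711} \times 0.995^{\text{age}} [\times 1.08 \text{ if black").

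**Step 1. Weights implied by the exponents above the cut-offs.** Creatinine: 0.601/1.209 = 0.497. Cystatin: 0.711/1.328 = 0.535. Each marker enters the combined equation at about half strength, so the remaining factors should lie near the geometric mean of the two single-marker equations.

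**Step 2. Test on the factors not in dispute.**

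| Factor | Geometric mean of single-marker values | Printed in combined |
|---|---|---|
| Age | √(0.993 × 0.996) = 0.9945 | 0.995 |
| Male constant | √(141 × 133) = 136.9 | 135 |
| Female constant | √(144 × 133 × 0.932) = 133.6 | 130 |

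The pattern holds to within about 3%.

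**Step 3. Apply it to race.**

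- Cystatin factor 1.00: √(1.159 × 1.00) = 1.077, which rounds to the printed 1.08. With the exponent weights it is 1.159^0.497 = 1.076.
- Cystatin factor 1.159: √(1.159 × 1.159) = 1.159. With the exponent weights it is 1.159^(0.497 + 0.535) = 1.165. Neither is near 1.08.
- Solving for the cystatin factor k in √(1.159 × k) = 1.08: k = 1.08²/1.159 = 1.006. If 1.08 was rounded from anywhere between 1.075 and 1.085, k runs from 1.075²/1.159 = 0.997 to 1.085²/1.159 = 1.016.

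The range includes 1.00 and is far from 1.159.

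**Step 4. Size in an affected subject.** Against k = 1.00 the overstatement is 1.159/1.00 − 1 = 15.9%. Against k = 1.006 it is 1.159/1.006 − 1 = 15.2%. Over the rounding range it runs from about 14% (k = 1.016) to 16% (k = 0.997).

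**Step 5. Size on the analysed quantity.** Illustrative man aged 45, cystatin C 1.6 then 1.4 mg/L (assumed values), with eGFR = 133 × (Scyst/0.8)^−1.328 × 0.996^45 × race, where 0.996^45 = 0.835:

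| Race factor | At 1.6 mg/L | At 1.4 mg/L | Change |
|---|---|---|---|
| 1.159 (as printed) | 51.27 | 61.21 | 9.95 |
| 1.00 | 44.23 | 52.82 | 8.58 |

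The excess change is 9.95 − 8.58 = about 1.4 mL/min/1.73 m² (1.365 before rounding). With one such subject in a group of four, the mean change moves by 1.365/4 = 0.34. In a Cohort 3 arm of nine (18 randomized 1:1) it moves by 1.365/9 = 0.15. The log change, ln(61.21/51.27) = ln(52.82/44.23) = 0.177, is the same either way.

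**The case against.** **The equations are separate.** A reader might take the table to prove the factor wrong. It does not: neither document says that the combined equation is derived from the other two, and neither reproduces a published source. That limit stands, so this is a strong inference and not a logical contradiction.

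**The halving pattern is not universal.** Below the cut-offs some exponents do not halve: cystatin 0.375/0.499 = 0.75, and female creatinine 0.248/0.329 = 0.75. That is true, but it does not rescue the printed factor. If 1.159 belonged to both single-marker equations, getting 1.08 would require the two weights to sum to ln 1.08/ln 1.159 = 0.52. The table's weights sum to at least 0.497 + 0.535 = 1.03, and the larger low-range weights only widen the gap.

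**A combined value outside its two parts is not diagnostic.** One could point to a Black man aged 40 with creatinine 1.5 mg/dL and cystatin C 1.3 mg/L. As printed he has 66.5 (creatinine), 68.9 (cystatin) and 62.1 (combined), so the combined value is below both. But over a grid of 3,240 combinations the combined value lies between its parts in only 93% of non-Black cases, where no race factor applies, and in 75% of Black cases as printed. The criterion would flag valid values and should not be used as a programming check.

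**Level shifts overstate the effect.** In that same man the cystatin value drops from 68.9 to 59.5 without the factor. A reader might carry over that shift, or the quarter of it that reaches the mean of a group of four (about 2.4), as the effect on the results. SAP section 12.8 analyses change from baseline, and the multiplier acts at both visits. The relevant figures are those of Step 5, and they shrink towards zero as the change itself does.

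**The practical effect may be nil.** The endpoint is exploratory, one of four eGFR versions, with no hypothesis tests (SAP section 12.3). Eligibility uses MDRD. The share of Black subjects is not given; the protocol notes that IgAN is less common in populations of African descent, and Cohort 3 has an Asian stratum. All of this stands. It limits the consequence but does not make the coefficient right.

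**Conclusion.** The point holds as an apparent transcription error in a pre-specified formula. Race is the one multiplicative factor checked that breaks the table's pattern, and it breaks it by repeating the creatinine value. Followed as printed, each cystatin-only eGFR and each absolute change in a Black subject is inflated by about 15 to 16%. This size assumes that the intended factor is 1.00, or the 1.006 implied by the table. The group-level figures also assume one affected subject with the illustrative cystatin values. The sign of a subject's change is unaffected, as are percent and log change, the other three equations, eligibility and non-Black subjects. No sample size, power or error-rate figure is involved.

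**What to change.** Check both CKD-EPI-Cyst rows of SAP Table 3 against the source equation. Remove the 1.159 race term from both rows unless the source supports it; if it does, say so. Cite the source of all the equations in the SAP, where the reference section is now empty. The cost is two table cells, a citation and one line of code, with no effect on data collection or trial conduct.

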12.9. Analysis of Other Efficacy Endpoints

Change in corticosteroid dose, based on milligrams of prednisone (or equivalent), from baseline to each scheduled visit will be summarized for each disease group for Cohort 1.

Change in serum creatinine from baseline to each scheduled visit will be summarized for each disease group, cohort and treatment. Nine-five percent CIs for the mean change from baseline will also be provided using t-distribution.

Duration of therapeutic response will be summarized descriptively by disease, cohort and treatment.

13. SAFETY AND TOLERABILITY

13.1. Overall Summary of Safety

An overall summary of treatment-emergent adverse events, which is defined as the AEs occurring or worsening after the start of study treatment, will be provided by disease group, cohort and treatment. All AEs will be coded by MedDRA. The following items will be included in the overall summary:

- Subject incidence of treatment-emergent AEs
- Subject incidence of treatment-related AEs (defined as probable or possible related to study drug)
- Subject incidence of treatment-emergent AEs by maximum CTCAE grade
- Subject incidence of treatment-emergent serious AEs (SAEs)
- Subject incidence of treatment-emergent AEs leading to discontinuation of study drug
- Subject incidence of treatment-emergent AEs leading to discontinuation of study
- Subject incidence of treatment-emergent fatal AEs
- Total number of unique treatment-emergent AE MedDRA preferred terms
- Median number of unique treatment-emergent AE MedDRA preferred terms per subject
- Total number of unique treatment-emergent SAE MedDRA preferred terms
- Median number of unique treatment-emergent SAE MedDRA preferred terms per subject

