9.1.2. Blinding

Cohort 1

No blinding is necessary for Cohort 1 since all subjects receive OMS721.

Cohort 2 and Cohort 3

Subjects in Cohort 2 and Cohort 3 will be randomized in a 1:1 fashion to receive either OMS721 or D5W vehicle control during the first 12 treatment weeks. Randomization for Cohort 3 will be stratified by region: North American and the United Kingdom in one strata and Asia in another strata. Study drug administration will be blinded. Additional treatment courses after the first 12 weeks in Cohort 3 will be open-label OMS721.

Treatment assignment will be blinded to all trial personnel, Omeros and its representatives, with the following exceptions:

- Investigative site pharmacist or designee who responsible for maintaining the blind at the site and will prepare and label the infusion.
- An independent site monitor (Clinical Research Associate), who will only monitor study drug accountability.
- Omeros CMC representative who will manage drug supply
- Omeros clinical data manager overseeing the implementation of the randomization module

In a medical emergency, it may be necessary to identify a subject's assigned treatment before the study has been completed and treatments unblinded. The treatment blind should only be broken if this information is necessary to treat the subject for a medical condition. In this situation, it is important that the treatment blind be maintained for all other subjects. The Omeros Medical Monitor should be contacted immediately if the treatment blind is broken. The date and reason for breaking the blind must be discussed with the Omeros Medical Monitor and recorded in the source documents.

CONFIDENTIAL

No use, disclosure or reproduction outside of Omeros without prior written authorization

Unblinding a subject's treatment assignment by the Investigator or study site personnel under any other circumstances (except as noted above) will be considered a protocol deviation.

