13.2.1. General Considerations

All data summaries will be descriptive in nature and summaries will be by disease and cohort, additionally safety information will be summarized overall for all subjects. Summary statistics for continuous variables will include number of subjects, mean, median, standard deviation, minimum, and maximum. For categorical variables, frequencies and percentages will be provided. When required for the statistical analysis of a particular variable, the baseline value will be the last recorded value prior to the administration of the first dose of study treatment. The exception is the urine albumin/creatinine and protein/creatinine ratios (Section [13.2.5](#)).

Statistical analyses will group subjects according to their assigned cohort, except for the rollover subjects who will constitute their own cohort.

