4.1. Sample Size Justification

The primary objective of the study is to assess safety and tolerability of OMS721. The sample size has been empirically determined. The study is not powered for statistical comparisons. Descriptive data summaries will be provided.

This is an exploratory study and the Cohort 1 sample size is considered clinically relevant to explore the effect of OMS721 in steroid-dependent IgAN, lupus nephritis, primary MN, and C3 glomerulopathy including dense deposit disease.

The sample size for Cohort 2 (subjects with IgA nephropathy who are not receiving corticosteroids) is considered clinically relevant to explore the effect of OMS721 in this population.

The sample size for Cohort 3 (subjects with IgA nephropathy who are not receiving corticosteroids) is considered clinically relevant to explore the duration of therapeutic response and the effect of additional courses of OMS721 treatment. The sample size for the Asian population residing in Asia in Cohort 3 is considered clinically relevant to explore the effect of OMS721 in this population.

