8. DEFINITIONS AND CONVENTIONS

8.1. Calculations Using Dates

Age at informed consent is calculated as the integer part of (date of informed consent – date of birth)/365.25.

Duration of treatment (days) is defined as (last dose date + 7 – first dose date). If a subject dies within 7 days of the last dose of study treatment, the duration of treatment is calculated as (death date – first dose date + 1).

Study day is defined as:

- Event Date – First Dose Date + 1 if the event date is on or after the first dose date
- Event Date – First Dose Date if the event date is before the first dose date

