10. SUBJECT DISPOSITION

The number of subjects treated, completing the protocol specified duration of study drug, discontinuing study drug early, completing the study, and early withdrawal from the study will be summarized by disease group. The reason(s) for early discontinuation of study drug and early withdrawal from the study will be summarized. The number of subjects in Cohort 1 and Cohort 2 who rollover to Cohort 3 will be summarized. A list of subjects failing any eligibility criteria will be provided.

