17. IMMUNOGENICITY ANALYSES

The presence of ADA will be summarized by disease, cohort and time. The presence of Nab will be summarized by disease, cohort and time.

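### The SAP has no rule for Cohort 3 adverse events after the first open-label OMS721 dose, and its duration formula and ADA summary mix off-drug time and vehicle with OMS721.

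*SAP*

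**What the plan says.** **Adverse events.** SAP 13.1 defines treatment-emergent events in the sentence that announces the table: "An overall summary of treatment-emergent adverse events, which is defined as the AEs occurring or worsening after the start of study treatment". The same sentence sets the grouping: disease group, cohort and treatment. SAP 13.2 uses the same grouping for the system organ class and preferred-term tables. Neither section gives an end date. Protocol 12.3.1 collects events up to the last follow-up visit, which for Cohort 3 is Follow-Up Visit 9, Day 722.

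**Open-label drug.** Protocol 9.1.2 randomises Cohorts 2 and 3 in a 1:1 ratio and adds: "Additional treatment courses after the first 12 weeks in Cohort 3 will be open-label OMS721". SAP Section 4 makes eligibility for these courses independent of the assigned arm. It allows them after the 6-week follow-up visit and again whenever the urine-protein criterion is met in Weeks 18 to 91. SAP 12.1 includes all data from randomised Cohort 3 subjects.

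**Exposure.** SAP 8.1: "Duration of treatment (days) is defined as (last dose date + 7 – first dose date"). The only exception is for death within 7 days of the last dose. Protocol 13.2.10.1 requires duration to be summarised.

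**Groupings without treatment.** SAP 17: "The presence of ADA will be summarized by disease, cohort and time", and the same for neutralising antibodies. SAP 10 says that completion, discontinuation and "early withdrawal from the study will be summarized by disease group". SAP 13.3 reports relative dose intensity by disease group only.

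**The concern.** A Cohort 3 subject has one randomised label but may receive two treatments. The SAP has no open-label category, no split of safety data by period and no cut-off at the first open-label dose. Its arm contrasts (SAP 12.6 to 12.8) name only OMS721 and vehicle. A programmer would therefore probably use the randomised arm throughout. Events that begin while a vehicle-randomised subject is on OMS721 would then appear in the vehicle column of the primary safety table.

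Independently of that, a table running to Day 722 compares arms over a long period in which most subjects may be off drug or free to take the same drug. This pulls the two columns together whatever the label rule.

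The duration formula was written for one uninterrupted course. After re-treatment it counts the off-drug interval as treatment and adds vehicle time to OMS721 time. An antibody rate for a whole randomised cohort includes subjects who have not yet received the antibody drug.

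**Working it through.** **1. The plan's own figure.** The initial course is 12 weekly doses, Day 1 to Day 78 (SAP 5.1). Last + 7 − first = 78 + 7 − 1 = 84 days = 12 weeks. The formula is exact for a single course.

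**2. The formula with one re-treatment course.** A course starting on Day s has its twelfth dose on Day s + 77. The formula gives (s + 77) + 7 − 1 = s + 83. Dosed days are 84 + 84 = 168. The earliest start is taken as Day 120 (target day of Follow-Up Visit 2, Week 18) and the latest as Day 631 (target day for Week 91).

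| Start day | Last dose | Formula (days) | Dosed days | Off-drug days counted | Formula ÷ 168 |
|---|---|---|---|---|---|
| 120 | 197 | 203 | 168 | 35 | 1.2 |
| 176 | 253 | 259 | 168 | 91 | 1.5 |
| 358 | 435 | 441 | 168 | 273 | 2.6 |
| 631 | 708 | 714 | 168 | 546 | 4.25 |

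For a vehicle-randomised subject only 84 of the 168 dosed days are on OMS721, so the formula is 203 ÷ 84 = 2.4 to 714 ÷ 84 = 8.5 times the time on OMS721.

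**3. How much of the event window is affected.** Days 120 to 722 are 603 of 722 study days, or 84%. Cohort 3 has about 18 subjects, so about 9 per arm. One vehicle subject whose only event occurs on open-label OMS721 changes vehicle incidence by 1 ÷ 9 = 11 percentage points.

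**4. Illustration of dilution (assumed rates, not from the documents).** Take a constant background rate b of 0.1 or 0.5 per year and a true on-drug rate ratio R of 2 or 3, with 84 drug days per course. Incidence is 1 − exp(−[R·b·drug days + b·other days] ÷ 365.25). For b = 0.1 and R = 3:

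- To Day 119: OMS721 1 − exp(−[0.3×84 + 0.1×35] ÷ 365.25) = 0.076; vehicle 1 − exp(−0.1×119 ÷ 365.25) = 0.032; ratio 2.36.
- To Day 722, nobody re-treated: OMS721 1 − exp(−[0.3×84 + 0.1×638] ÷ 365.25) = 0.216; vehicle 1 − exp(−0.1×722 ÷ 365.25) = 0.179; ratio 1.21.
- To Day 722, everyone in both arms re-treated once: 0.251 against 0.216; ratio 1.16.

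Over all combinations of b and R, the ratio is 1.6 to 2.4 to Day 119. To Day 722 it is 1.06 to 1.21 with no re-treatment and 1.05 to 1.19 when 25% to 100% of both arms are re-treated once. If every vehicle subject and no OMS721 subject takes one course, both arms have 84 drug days and the ratio is exactly 1.00. Most of the dilution comes from long common follow-up; open-label use in the vehicle arm removes what is left, to a degree that depends on how unequal it is.

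**5. Antibodies.** With 1:1 allocation, if a proportion p of OMS721 subjects and no vehicle subjects are positive, the cohort figure is p ÷ 2. An assumed 20% would be reported as 10%. This holds for Cohort 2, and for Cohort 3 before any vehicle subject takes open-label drug. Cohort 1 has no vehicle arm and is not affected.

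**The case against.** Several points on the other side have force.

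- A reader might infer that the SAP assigns every event to Week 104 to the randomised arm. It does not say so. It leaves treatment undefined, and the table shells, a separate document (SAP 20.1), may settle the matter. This stands as a limit on the claim: the fault is a missing rule. An attribution rule for the primary endpoint nevertheless belongs in the SAP.
- A reader might infer that the long durations distort adverse event rates. They do not. Every rate in SAP 13.1 and 13.2 is subject incidence, and the dose counts in SAP 13.3 are not inflated by off-drug gaps. The formula affects only the duration summary, and only in re-treated subjects.
- A reader might infer that open-label use is what chiefly hides a drug effect. The illustration does not support that: long common follow-up does most of it.
- The analyses planned after the 6-week follow-up (SAP 18) give a mostly pre-re-treatment view. But that section fixes when an analysis is run, with no cut-off per subject. Those who enrolled early may already be on open-label drug when the last subject reaches that visit.
- SAP 12.1 restricts Cohorts 1 and 2 to the initial periods, so the Week 104 problem concerns Cohort 3. That text is under efficacy and is not repeated for safety. Laboratory values and vital signs are tabulated by visit, so their rows before Follow-Up Visit 2 already precede Cohort 3 open-label dosing; the split matters most for adverse events.
- SAP 12.4 says that analyses are by disease group, cohort and treatment, so the omission of treatment in SAP 10, 13.3 and 17 may be shorthand. SAP 12.4 is also in the efficacy section, and SAP 17 as written pools the arms.
- The trial is descriptive: "The study is not powered for statistical comparisons". That lowers the stakes for inference, but a descriptive table must still show which drug a subject was on.

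**Conclusion.** The point holds for Cohort 3 as a missing attribution rule, with two stated rules that give misleading results if followed. Events on open-label OMS721 in vehicle-randomised subjects fall in the vehicle column if treatment means the randomised arm, which is the natural but not the stated reading. One misplaced subject is worth 11 percentage points with about 9 per arm. Duration of treatment is overstated 1.2- to 4.25-fold for a subject with one re-treatment course starting between Days 120 and 631, and is correct for subjects never re-treated. The antibody summary understates the OMS721 rate by half in Cohort 2, and in Cohort 3 before open-label use, if vehicle subjects are negative. The dilution figures depend on assumed rates and on how many subjects are re-treated, which the documents cannot give.

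Protocol 13.2.1 also promises that "additionally safety information will be summarized overall for all subjects", which SAP Section 13 does not provide and SAP 21.1 does not list as a change. A reader might take this for a further safety gap. It is a minor mismatch between the two documents and changes none of the results above.

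**What to change.** Amend the SAP as follows.

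1. **SAP 13.1 and 13.2, blinded period.** Present Cohort 3 treatment-emergent events by randomised arm from the first dose to the earlier of Follow-Up Visit 2 and the first open-label dose.
2. **SAP 13.1 and 13.2, open-label period.** Present events from the first open-label OMS721 dose separately, by randomised arm, with rates per person-time as well as subject incidence.
3. **SAP 8.1.** Compute duration for each course as last − first + 7 and sum over courses, separately for OMS721 and vehicle. One re-treatment course then gives 84 days of vehicle plus 84 of OMS721 for a vehicle-randomised subject, and 168 of OMS721 for an OMS721-randomised subject, whatever the start day.
4. **SAP 17.** Add treatment to the ADA and neutralising antibody summaries, and time results from each subject's first OMS721 dose.
5. **SAP 10 and 13.3.** Add cohort and treatment to disposition and to relative dose intensity.
6. **Minor.** Restore the overall safety summary or record its omission in SAP 21.1.

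The cost is SAP wording, table shells and programming. Dosing dates and event onset dates are already collected, so no new data are needed. The downside is more tables with small cells, about 9 subjects per arm.
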